### 5.2 Study Population

#### 5.2.1 Inclusion criteria

1. Age: patients must be  $\geq 18$  years of age and  $\leq 30$  years of age at the time of study entry.
2. Diagnosis: Patients must have documented diagnosis of Hemoglobin SS Disease or S-Beta 0 Thalassemia by either HPLC or Hemoglobin Electrophoresis
3. Disease status: Patients must have at least 2 documented episodes of vaso-occlusive pain in the prior year as defined by an acute episode of pain lasting greater than 24 hours, with no medically determined cause other than a vaso-occlusive event that resulted in treatment with oral or parenteral opiates or with a parenteral nonsteroidal anti-inflammatory drug.
4. Performance Level: Karnofsky  $\geq 80$  for patients  $> 10$  years of age and Lansky  $\geq 80$  for patients  $\leq 10$  years of age. Patients who are unable to walk because of paralysis, but who are up in a wheelchair, will be considered ambulatory for the purpose of assessing the performance score.
5. Organ function requirements:

- a. Adequate bone marrow function defined as
  - i. Peripheral absolute neutrophil count (ANC)  $\geq 1000/\mu\text{L}$
  - ii. Platelet count  $\geq 100,000/\mu\text{L}$  (transfusion independent)
- b. Adequate renal function defined as
  - i. Creatinine clearance or radioisotope GFR  $\geq 70 \text{ mL/min}/1.73 \text{ m}^2$  or
  - ii. A serum creatinine based on age/gender as follows

**Table 1:** Maximum serum creatinine allowed for eligibility

Age	Maximum Serum Creatinine (mg/dL)	
	Male	Female
2 to <6 years	0.8	0.8
6 to <10 years	1	1
10 to <13 years	1.2	1.2
13 to <16 years	1.5	1.4
$\geq 16$ years	1.7	1.4

The threshold creatinine values were derived from the Schwartz formula for estimating GFR (Schwartz et al. J. Peds, 106:522, 1985) utilizing child length and stature data published by the CDC.

- c. Adequate Liver Function Defined As:
  - i. SGPT (ALT  $< 2.5$  upper limit of normal. For the purpose of this study, the ULN for SGPT is 45 U/L)
  - ii. Serum albumin  $\geq 2 \text{ g/dL}$
- d. Adequate cardiac function defined as:
  - i. Shortening fraction or ejection fraction greater than the LLN (institutional norm), and
  - ii. Corrected QT interval  $\leq 450 \text{ msec}$

6. Informed Consent: All patients must sign a written informed consent. Assent, when appropriate, will be obtained according to institutional guidelines.

### 5.2.2 Exclusion criteria

1. Chronic transfusion protocol.
  - a. Patients currently on a chronic transfusion protocol are not eligible
2. Hydroxyurea Intolerance
  - a. Patients who are ineligible for hydroxyurea due to persistent marrow suppression (e.g. thrombocytopenia, neutropenia)
3. Pregnancy or Breast-Feeding
  - a. Pregnancy tests must be obtained in girls who are post-menarchal. Males or females of reproductive potential may not participate unless they have agreed to use an effective contraceptive method.
4. Concomitant Medications
  - a. Investigational Drugs: Patients who are currently receiving another investigational drug.
  - b. Anti-cancer agents: Patients who are currently receiving other anti-cancer agents.
  - c. The following CYP3A4 inducers are prohibited 14 days before the start of imatinib and during the study with imatinib: rifampin, rifabutin, carbamazepine, Phenobarbital, phenytoin, St. John's wort, efavirenz, and tipranavir.

- d. The following CYP3A4 inhibitors are prohibited 7 days before the start of imatinib and during the study with imatinib: azole antifungals (itraconazole, ketoconazole); clarithromycin, erythromycin, diltiazem, verapamil, HIV protease inhibitors (indinavir, saquinavir, ritonavir, atazanavir, nelfinavir); delavirdine.
- 5. Patients who have an uncontrolled infection.
- 6. Prior use of Imatinib: Patients who have previously received imatinib are not eligible for study.
- 7. Patients who in the opinion of the investigator may not be able to comply with the safety monitoring requirements of the study.
- 8. Patient is < 5 years free of a malignancy. Existence of any other malignant disease is not allowed.
- 9. Patient with Grade III/IV cardiac problems as defined by the New York Heart Association Criteria. (i.e., congestive heart failure, myocardial infarction within 6 months of study).
- 10. Patients with a history of QT prolongation, need for concomitant use of anti-arrhythmics or other agents known to prolong QT interval, or electrolyte derangement that cannot be corrected to within normal limits prior to initiation of study drug.
- 11. Patients with a family history of sudden cardiac death.
- 12. Patient has a severe and/or uncontrolled medical disease other than sickle cell disease (i.e., uncontrolled diabetes, chronic renal disease, or active uncontrolled infection).
- 13. Patient has known chronic liver disease (i.e., chronic active hepatitis, and cirrhosis).
- 14. Patient has a known diagnosis of human immunodeficiency virus (HIV) infection.
- 15. Patient had a major surgery within 2 weeks prior to study entry.

### **5.3. Sample Size**

A total of 40 participants will be enrolled. Thirty subjects will be recruited at Riley Hospital for Children with 10 of the subjects having sickle cell anemia and up to 20 normal donor subjects enrolled for specimen shipping purposes. Ten subjects with sickle cell anemia will be recruited at Cincinnati Children's Hospital. This sample size has been determined by the primary endpoints (See Section 15 for details).

### **5.4 Recruitment Strategy**

Subjects will be recruited through the Pediatric Hematology/Oncology clinic at Indiana University School of Medicine, Pediatric Hematology/Oncology clinic at Cincinnati Children's Hospital and Cincinnati CTSI. Study subjects will be compensated for their participation with a \$50 gift card provided at the end of each monthly visit.

## **6.0 TREATMENT PROGRAM**

All patients with sickle cell anemia will be treated in the same group. There will not be a randomization.

Patients will receive Imatinib orally once daily for 6 months.

The starting dose for subjects will be 340 mg/m^2/day with a maximum dose of 600 mg daily. Drug doses will be rounded to nearest 50 mg according to the dosing table in Appendix A. Dosing should be based on the body surface area (BSA) obtained at each clinic appointment. Drug will be dispensed as a 30-day supply at each visit. Patients will be asked to bring the prescription bottle with them to each visit to assist with monitoring compliance.

Clinic visits will occur at initiation of imatinib and then every 30 days +/- 7 days. Monthly visits will consist of interim history, assessing for adverse side effects and compliance. Participants will be asked to have blood drawn (see Section 11) 2 weeks +/- 3 days after initiation of the drug. Additionally, during the first two months of drug administration, patients will be called or texted a survey link weekly for follow-up safety assessments, except for the participant's in-clinic visits at week 2, 4 and 8. The survey link will come via an app, called Twilio, that allows REDCap the capability to send SMS text messages to survey respondents. If the patient is unable to be reached by phone for at least 3 of the 4 weekly assessments each month, they will be asked to be seen in clinic for a safety assessment. If the patient is unable to do so, they will be removed from protocol therapy for protocol non-compliance. The 1 month, 3 month, 6 month, and 1-month off-therapy visits will consist of a comprehensive history and physical

exam, as well as laboratory and diagnostic studies documented in Section 10. The other visits (2, 4 and 5-month visits post treatment initiation) will be research-nurse visits, with a provider available to sign the next month's prescription.

Patients will be given a copy of the "Patient Pain Journal" at each visit which will need to be completed and returned at the next visit. This journal should be reviewed with the treating physician and/or research nurse at each clinic appointment while on study. Patients should be instructed to use the journal to record any occurrence of pain episodes (see definition in Section 5.3), the duration, and necessary interventions. They will be asked to score their pain on a scale of 1-10. Additionally, it will be used to record the date and time of each imatinib dose as well as observed side effects and supportive treatments used while on study.

Opioid use, hospitalizations, and occurrence of acute chest syndrome (see definitions in Section 5.3) will be reviewed at each study visit, as well. This information will also be extracted from the EMR at each site to confirm patient/guardian report.

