## **6.1 Dosage:**

Mylan will supply Imatinib as 100 mg tablets packaged in bottles for an exposure period of up to 6 months or so long as the patient remains on study. The starting dose for subjects will be 340 mg/m^2 with a maximum dose of 600 mg daily. Tablets can be broken in half, and therefore, drug doses will be rounded to nearest 50 mg according to the dosing table in the Appendix A. Dosing should be based on the body surface area (BSA) obtained at each clinic appointment.

The prescribed dose should be administered at the same time each morning, orally, with a meal and a large glass of water. Patients should keep normal eating habits, however a low-fat (i.e. continental) breakfast is recommended and avoiding xanthine (e.g. caffeine) or grapefruit containing food or beverages. If vomiting occurs > 15 minutes after administration of the dose, no additional trial medication should be taken that day in an effort to replace the material that has been vomited.

In the absence of dose limiting toxicity (DLT), patients may receive a total of 6 months of therapy. Continuing treatment beyond this period will be at the discretion of the investigator and may become the financial responsibility of the patient if no alternative method of obtaining or paying for the drug can be identified at that time. Medication labels will comply with the legal requirements of the US and will be printed in English. The storage conditions for Imatinib will be described on the medication label. Bottles must be stored in a safe, secure location.

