## **11.0 EVALUATIONS/MATERIAL AND DATA TO BE ACCESSIONED**

Subjects will be prescreened for potential eligibility prior to initial clinic visit. All entry/eligibility laboratory and imaging studies will be performed at or within 2 weeks of the initial visit. Baseline EKG to rule-out prolonged QTc, and if needed, echocardiogram, is required within 2 weeks of starting protocol therapy. If eligibility studies are drawn but the participant was not able to be enrolled/initiate study drug (e.g. hospitalized) in this timeframe, all eligibility laboratory studies will need to be repeated. EKG and ECHO do not need repeated unless there are new clinical concerns. Each study visit will occur approximately 4 weeks (+/- 1 week) after the previous.

STUDIES TO BE OBTAINED	Baseline	2 Weeks	1 Month	2 Months	3 Months	4 Months	5 Months	6 Months	1 month Off Study
Phone Assessment (Weekly)			X	X					
History	X		X	X	X	X	X	X	X
Physical exam with vital signs	X		X		X			X	X
Height, weight, BSA	X		X	X	X	X	X	X	X
Performance Status	X		X	X		X	X		
CBC/platelet with differential, Reticulocyte Count	X	X	X	X	X	X	X	X	X
HPLC or Hemoglobin EP	X								
Ektacytometry, OxygenScan, F% correlation, Blood Viscosity#	X		X		X			X	X
% ISCs (irreversibly sickled cells)	X		X		X			X	X
D-dimer	X		X		X			X	X
Urine Pregnancy test (female)	X		X		X			X	
CMP^, Mag, Phos, Uric Acid, Amylase, Lipase and tryptase	X		X		X			X	X
Biochemical Analysis Sample	X		X		X			X	X
EKG*	X								X
Echocardiogram*	X								
Patient Pain Journal			X	X	X	X	X	X	X
Concomitant Medication Assessment	X	X	X	X	X	X	X	X	X

**Table 2.** Studies to confirm eligibility and monitor safety and efficacy on imatinib

\*During study treatment, monitor for signs and symptoms of arrhythmia and for edema and fluid retention that may cause congestive heart failure. Obtain EKG/echocardiogram and cardiology consult as clinically indicated.

#Blood samples for these studies to be sent to Cincinnati

[figure not shown]
^CMP should include Albumin, Alkaline phosphatase, ALT (SGPT), AST (SGOT), BUN, Calcium, Chloride, Carbon Dioxide, Creatinine, Glucose, Potassium, Sodium, Total Bilirubin, Total Protein, and a calculation of eGFR.

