## **13.0 CRITERIA FOR REMOVAL FROM PROTOCOL THERAPY**

1. Adverse Events requiring removal from study
2. Refusal of further protocol therapy by patient/parent/guardian.
3. Non-compliance that in the opinion of the investigator does not allow for ongoing participation, including <70% of drug prescribed being taken. Compliance will not be contingent on completion of the pain journal as this not the primary endpoint of the study.
4. Physician determines continued protocol therapy is not in the patient's best interest.

Patients who are off protocol therapy are to be followed until they meet the criteria for Off Study (see below). Ongoing adverse events, or adverse events that emerge after the patient is removed from protocol therapy, but within 30 days of the last dose of investigational agent, must be followed and reported via RDE and AERS (if applicable). Follow-up data will be required unless consent is withdrawn.

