## 15.4 Efficacy evaluation

Descriptive statistics will be calculated for all endpoints before, during, and after treatment. Changes before and 6 months after treatment in biochemical endpoints will be tested with two-sided paired t-tests. This analysis will be supplemented with single group repeated measures ANOVA to test for effects over time since there are 3 measures on treatment. Many secondary endpoints are counts (e.g. frequency of refills of opioids, number of hospitalizations). Depending on the distributions of these outcomes, we will either: 1) dichotomize and compare with McNemar's test; 2) treat as ordinal and compare with a Cochran-Mantel-Hazensel type test; or 3) treat as continuous and conduct either paired t-test or Wilcoxon signed rank tests. Since the pain measure will depend on age, we will only statistically analyze when there are at least 6 participants using a single-group repeated measures ANOVA model. Otherwise, only graphical descriptions will be used.

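### A 30-day supply does not reach the late end of either visit window, so an adherent, in-window patient can be out of drug when an on-treatment sample is drawn (minor, cheap to fix)

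*Combined protocol and SAP*

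**What the plan says.** Section 6.0 sets the supply: "Drug will be dispensed as a 30-day supply at each visit". It also sets the schedule: "Clinic visits will occur at initiation of imatinib and then every 30 days +/- 7 days". It does not say whether the window is counted from first dose or from the previous visit. Section 11.0 gives a different rule: "Each study visit will occur approximately 4 weeks (+/- 1 week) after the previous".

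Table 2 in Section 11.0 schedules the "Biochemical Analysis Sample" at baseline, Months 1, 3 and 6, and one month off study. The functional red-cell tests and the percentage of irreversibly sickled cells follow the same columns.

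Section 15.4 names the main test: "Changes before and 6 months after treatment in biochemical endpoints will be tested with two-sided paired t-tests". It adds a repeated measures ANOVA "to test for effects over time since there are 3 measures on treatment".

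Three other passages bear on the point. Section 13.0 allows removal for non-compliance, "including <70% of drug prescribed being taken". Section 6.1 says of dosing past six months: "Continuing treatment beyond this period will be at the discretion of the investigator". Section 12.0 gives half-lives of about 18 hours for imatinib and 40 hours for its active metabolite. No passage gives an overage, an interim refill, a rule on leftover tablets, or a maximum time between last dose and sample.

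**The concern.** The supply matches the target interval but not the tolerance around it. A patient who takes every dose and attends late, yet within the window, runs out before the visit. At Month 1 there is no earlier stock to draw on. The patient then has an avoidable treatment interruption, and the blood sample enters the analysis as an on-treatment measure although dosing has stopped.

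An endpoint that reverts within days would show a diluted effect. Missed doses leave spare tablets, so run-out falls on the most adherent patients, who should show the drug's effect best.

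**Working it through.** **The plan's own figure.** Section 15.1 gives mean 140,000, SD 75,000, a fall of 70,000, correlation 0.5, n = 20 and two-sided alpha 0.01. The SD of the difference is 75,000 × √(2 × (1 − 0.5)) = 75,000. The noncentrality is 70,000/75,000 × √20 = 4.17 on 19 df. Power is 0.890, so the stated 89% reproduces.

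**Largest gap at Month 1.** Section 6.0: 37 − 30 = 7 days. Section 11.0: 35 − 30 = 5 days. This needs no assumption about visit timing.

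**Share of Month 1 visits after run-out.** At adherence *a*, 30 days of tablets last 30/*a* days. The latest visit day L is 35 (Section 11.0) or 37 (Section 6.0).
- Uniform timing: share = (L − 30/*a*)/14. With *a* = 1 this is 5/14 = 36% or 7/14 = 50%, about 7 to 10 of 20 patients. With *a* = 0.95 it is (L − 31.58)/14 = 24% or 39%.
- Triangular timing, peaked at the target day: beyond the target, share = (L − 30/*a*)²/98. With *a* = 1 this is 25/98 = 26% or 49/98 = 50%.

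**Gaps of 3 days or more at Month 1, *a* = 0.95.** The threshold is 31.58 + 3 = 34.58 days.
- Uniform: 0.42/14 = 3% or 2.42/14 = 17%.
- Triangular: 0.42²/98 = 0.2% or 2.42²/98 = 6%.

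**Adherence needed for any Month 1 run-out.** It is above 30/35 = 86% or 30/37 = 81%. At the 70% level in Section 13.0 the tablets last 30/0.7 = 43 days, so there is none.

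**Later visits.** These were simulated with uniform timing, 30 days dispensed at initiation and at Months 1 to 5, and leftovers kept:

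| Visit rule | Month 3, *a* = 1 | Month 3, *a* = 0.95 | Month 6, *a* = 1 | Month 6, *a* = 0.95 |
|---|---|---|---|---|
| Section 11.0 | 12% | 4% | 4% | 0.5% |
| Section 6.0, from first dose | 29% | 9% | 16% | 0% |
| Section 6.0, from previous visit | 31% | 15% | 23% | 7% |

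If leftovers are collected at each visit, Month 6 matches Month 1 (36% to 50% with full adherence). If windows also run from first dose, an early visit followed by a late one leaves 44 days on 30 days of tablets, a gap of up to 14 days.

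**Drug remaining,** relative to the level when the next dose was due: 0.5^(24d/18) for imatinib and 0.5^(24d/40) for the metabolite, after d days. One day leaves 40% and 66%; 3 days leaves 6% and 29%; 7 days leaves 0.2% and 5%.

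**Check of the remedy.** With windows counted from first dose, 37 days then 30 gives cumulative supply of 37 + 30(k − 1) = 30k + 7 days before visit k. That equals the latest day of visit k, so run-out is zero (simulated 0.0%). If windows stay chained to the previous visit, one 7-day reserve still leaves Month 6 run-out at about 2% (Section 11.0) to 15% (Section 6.0) with full adherence. Dispensing 37 days at every visit gives 0%.

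**The case against.** A reader might infer that up to half of the Month 1 samples are effectively drug-free, that the Month 6 result is compromised, or that an effect seen to build over time would be an artefact of supply. The documents do not support these readings.

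- **Short gaps count as run-out.** The shares include any sample taken after the next dose was due, even by hours, and much of the drug is still present a day later. Gaps of 3 days or more are far fewer.
- **Timing is assumed.** Visits usually cluster near the target date, which lowers the shares. Section 6.0 also places the early in-clinic visits at weeks 2, 4 and 8. That puts Month 1 at about day 28 and favours the smaller Section 11.0 figures.
- **Reversion is unknown.** No reversion rate is stated for any primary endpoint. Section 3.4 chose six months partly to allow time for slow change, citing irreversibly sickled cells, so at least that endpoint may barely notice a gap of days. Any percentage attenuation would be invented.
- **The main test uses Month 6.** Month 1 enters only a supplementary ANOVA in a 20-patient pilot, and no hypothesis about trajectory is planned.
- **Detail may sit elsewhere.** Section 6.2.1 delegates dispensing to the investigational pharmacy, which has its own manual. Section 6.1 does not cap supply at 180 days. The weekly contacts in the first two months could catch a run-out.

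These points stand, and they make the matter minor. They do not remove it. The written rules, followed exactly, permit the gap. The weekly contacts are described as safety checks, with no refill. Dispensing at week 2 is unlikely, because Table 2 has no body surface area at that visit and prescriptions are described as monthly.

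**Conclusion.** The mismatch is certain, and its consequence is limited. An adherent, in-window patient can be without drug for up to 7 days (Section 6.0) or 5 days (Section 11.0) at a draw that the analysis treats as on treatment.

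The frequencies are ranges under assumed visit timing and are not predictions. The finding that Month 6 is less exposed than Month 1 depends on patients keeping unused tablets, and the documents do not say whether they do. Any bias is toward no effect and cannot be sized. The power statement needs no change. This is a minor improvement, worth making because it is cheap and also spares patients an interruption.

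**What to change.** Use one schedule in Sections 6.0 and 11.0, with windows counted from first dose: visit k at day 30k ± 7. Dispense 37 days at initiation (38 if the visit-day dose must be covered) and 30 days at each later visit. Let patients keep leftover tablets, and tell them to continue dosing until the Month 6 sample is drawn. If the pharmacy manual already covers this, one confirming sentence in Section 6.0 is enough.

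If windows must stay chained to the previous visit, dispense 37 days at every visit, because a single reserve does not suffice.

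The cost with anchored windows is at most 7 days × 6 tablets = 42 extra tablets per patient at 600 mg (48 with 38 days). With 37 days at all six dispensings it is up to 6 × 42 = 252. The compliance tablet count must allow for the reserve, and scheduling becomes slightly tighter. Sample size, monthly dosing review and safety review are unchanged.

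### The 3-of-4 non-contact rule in Section 6.0 does not fit its own schedule of two remote contacts in month 1 and three in month 2

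*Combined protocol and SAP*

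**What the plan says.** For the first two months on imatinib, Section 6.0 states that "patients will be called or texted a survey link weekly for follow-up safety assessments". It exempts the participant's "in-clinic visits at week 2, 4 and 8".

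The non-contact rule follows: "If the patient is unable to be reached by phone for at least 3 of the 4 weekly assessments each month", then "they will be asked to be seen in clinic for a safety assessment". For a patient who cannot come in, the outcome is that "they will be removed from protocol therapy for protocol non-compliance".

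On visits and supply, Section 6.0 says "Clinic visits will occur at initiation of imatinib and then every 30 days +/- 7 days" and "Drug will be dispensed as a 30-day supply at each visit". Section 11.0 gives a slightly different interval: "Each study visit will occur approximately 4 weeks (+/- 1 week) after the previous".

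Table 2 in Section 11.0 marks a weekly phone assessment under month 1 and month 2 but gives no number of calls. Section 13.0 leaves non-compliance to the investigator's opinion and does not mention calls. No section says whether an attended clinic visit counts toward the four, or whether a returned text survey counts as being reached.

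**The concern.** The rule counts four phone assessments a month, but the schedule in the same paragraph has fewer than four in both months. The wording also leaves open whether the threshold of 3 counts failures or successes. In month 1 those two readings give opposite results: one calls in nobody and the other calls in everybody.

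The rule decides who is brought in early for a safety check during the first two months on drug and, after that, who may be taken off therapy. Section 5.3 plans ten patients with sickle cell anemia at each of two sites, and the sites could apply the sentence differently while both believed they were following it.

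**Working it through.** **Count of remote contacts (Section 6.0).** The plan's figure is 4 each month. From the schedule:

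- Month 1: weeks 1 to 4, less clinic weeks 2 and 4, leaves weeks 1 and 3. 4 − 2 = 2 contacts.
- Month 2: weeks 5 to 8, less clinic week 8, leaves weeks 5, 6 and 7. 4 − 1 = 3 contacts.

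The 4 is not reproduced in either month. The visit windows do not change the planned count.

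**What triggers the rule under each reading**, with scheduled visits attended:

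| Reading | Month 1 | Month 2 |
|---|---|---|
| A. Calls only, 3 or more missed | never (at most 2 can be missed) | all 3 missed |
| A′. Attended visits included in the 4, 3 or more missed | never (at most 2 of 4 missed) | all 3 calls missed |
| B. Calls only, at least 3 must be reached | always (at most 2 can be reached) | any 1 missed |
| C. Attended visits count, at least 3 of 4 contacts must be made | both calls missed (2 visits + 0 calls = 2) | 2 or 3 of the 3 calls missed (1 visit + at most 1 call = 2) |

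Only C gives a usable rule in both months. Counting visits is not enough by itself: under A′ month 1 still cannot trigger.

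**Illustration of how far the readings differ.** The documents give no miss rate. Assume each call is missed independently with probability p = 0.1, 0.2 or 0.3, in 20 treated patients (Section 15.1).

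- A: month 1 is 0 and month 2 is p³ = 0.001, 0.008, 0.027. Times 20 = 0.02, 0.16, 0.54 requests over two months.
- B: month 1 is 1 and month 2 is 1 − (1 − p)³ = 0.271, 0.488, 0.657. 20 × (1 + month 2) = 25.42, 29.76, 33.14 requests.
- C: month 1 is p² = 0.010, 0.040, 0.090 and month 2 is 3p²(1 − p) + p³ = 0.028, 0.104, 0.216. 20 × the sum = 0.76, 2.88, 6.12 requests.

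If misses cluster completely (a patient misses all calls or none), A and C call in the same month-2 patients, but A does so one week later and still calls in nobody in month 1.

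**Time between a flag and the next visit**, assuming calls on days 7, 21, 35, 42 and 49:

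| Flag | 30 ± 7 days (Section 6.0) | 4 weeks ± 1 week (Section 11.0; month-1 visit on day 28) |
|---|---|---|
| After week 3 (day 21) | visit day 23–37: 2–16 days | visit day 21–35: 0–14 days |
| After week 6 (day 42) | visit day 53–67: 11–25 days | visit day 49–63: 7–21 days |

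Dispensing shortens the time on drug. With full adherence from day 1 and no break between supplies, the first supply ends about day 30 and the second about day 60. Drug in hand then lasts about 30 − 21 = 9 days after a week-3 flag and 60 − 42 = 18 days after a week-6 flag. Missed doses or a late month-1 visit would move these later.

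**The case against.** The best defence is that the paragraph plans weekly safety assessments and omits the call in weeks 2, 4 and 8 because the patient is being seen. That makes four assessments a month. The reference to the phone is loose anyway, since a texted survey is allowed. Read as at least 3 of 4 made, the rule already has the thresholds recommended below. This largely stands: the change clarifies a workable intention and is not a redesign. But the text neither counts visits nor says that 3 must be made, and a reader who takes it as 3 missed gets no month-1 trigger even with visits counted.

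A reader might infer, without qualification, that the rule is dead in month 1. The documents do not support that. It follows from the 3-missed reading, and the 3-reached reading by phone alone gives the reverse.

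A reader might also infer that silent patients go unmonitored on drug for up to 16 or 25 days. Those are the extremes of the wider visit window and ignore the dispensing limit. Section 6.0 treats week 2 as a clinic visit in place of the call. Table 2 marks only blood counts and concomitant medications then, but that does not rule out a symptom check. Section 15.3 monitors dose-limiting toxicity continuously, Section 18.1 adds continuous investigator review of safety, and Section 13.0 lets the investigator end therapy in the patient's interest.

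Finally, any stated frequency of missed flags would rest on assumed miss rates. The figures above show only how far the readings diverge.

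**Conclusion.** The rule is wrong as written. It states a denominator of 4 phone contacts where the schedule provides 2 and then 3, and nothing elsewhere in the document corrects this. The counts need no assumption. The conclusion that only one reading works in both months assumes that scheduled visits are attended.

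The size is minor. A workable rule would add a prompt after silence in weeks 1 and 3. It would also flag a patient silent in weeks 5 and 6 after week 6, where the 3-missed reading waits for week 7 and needs that call missed too. The rule plays no part in the paired t-tests, the alpha of 0.01 or the sample size of 20, so a reader should not carry this point over to the efficacy analysis.

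**What to change.** Restate the rule on the contacts actually planned, for example: *A patient who misses both remote contacts in month 1 (weeks 1 and 3), or two or more of the three in month 2 (weeks 5, 6 and 7), is invited to clinic for a safety check. This equals fewer than 3 of 4 weekly contacts when attended clinic visits are counted. A returned text survey is a contact.* Keep removal only for patients who cannot attend. Changing the denominator alone is not enough, because a threshold of 3 still cannot work with 2 contacts in month 1. The investigators should confirm the thresholds and say whether a scheduled visit that is nearly due may serve as the check.

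The cost is a sentence or two of text and a few extra requests: 0.76, 2.88 or 6.12 across 20 patients under the illustrative miss rates. Of these, the requests raised after week 6 number 20p² = 0.2, 0.8 or 1.8 and would most clearly need a separate visit. The remaining 74%, 72% or 71% arise after week 3 or week 7, shortly before the week 4 or week 8 visit.
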